- (4) Able to follow instructions to interact in simple computer games

Sample size calculation: There is no previous published study using the primary outcome measure (see below under Methods) to examine the effect of the ICP on trunk control in this population group, hence, no sample size calculation is possible based on previous data. Thus it is estimated that 20 children with 10 children in each arm for this pilot RCT is appropriate and feasible. The sample size will be the largest among the previous studies in this area.

Exclusion criteria:

- (1) Children with epilepsy/ seizures that could be elicited by flashing lights or sudden loud noises from computer screens

(ii) Methods

Outcome measures (OM) used in this proposal include:

Primary study outcome:

- (1) Segmental Assessment on Trunk control (SATCo)^[8] assessment on the child's segmental trunk control by progressively reducing the trunk support from the shoulder girdle to assess the

head control, through support at the axillae (upper thoracic), inferior scapula (mid-thoracic), lower ribs (lower thoracic), below ribs (upper lumbar), pelvis (lower lumbar) and no support to measure full trunk control.^[8] The trunk control is tested under 3 different conditions in sitting: to maintain the posture (static control), during voluntary head movements (active control) and recovery of trunk control after a disturbance of balance by a nudge (reactive control).^[8]

Secondary study outcomes:

(2) Pediatric Reach Test (PRT)^[22] assessment on balance in sitting and standing positions. The distance how far the child can reach forward, to right and to left will be measured in sitting and standing. High construct validity has been shown between the PRT in standing and a laboratory test of steadiness in quiet stance ($r= 0.79$) and age ($r= 0.83$) in a group of 19 typically developing children. High construct validity has also been shown between the total PRT score and GMFCS level ($r= 0.88$) among a sample of 10 children with cerebral palsy. Test-retest reliability and inter-tester reliability with children with cerebral palsy was moderate to high (intraclass correlation coefficients= 0.54 to 0.88 and 0.50 to 0.93 respectively)^[22] and

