(3) Gross Motor Function Measure 88 (GMFM 88)^[23] assessment on general gross motor function in various positions including lying, sitting, 4-point kneeling, high kneeling and standing. The intra- and inter-rater reliability of the GMFM 88 have been shown to be very high (ICC= 0.99 in both cases).^[23]

(4) 2-minute walk test^[24] distance covered in a period of 2 minutes with self-chosen comfortable speed will be measured. The walk test has been shown to have high test-retest, intra- and inter-rater reliability.^[24]

(5) The height and weight of the children

(iii) Study design

20 children with CP or similar physical disabilities will be recruited from 2 special schools for children with physical disabilities in Hong Kong for this pilot RCT (see 'Existing facilities' for details). Informed consent will be sought from the parents or guardians before the study will commence. After the initial assessment, all study children will be randomly allocated into a control group or treatment group (10 children in each arm) using a 'draw card from the hat'. The randomization will be separately done in each school so as to take into account the heterogeneity of the children and treatment regime in each school. The children in the treatment group will receive training on their trunk control using the Tymo in sitting 4 times per week for 20 minutes per session. The treatment will last for 6 weeks. All study children will continue their usual therapies at school but will be asked to stop playing any interactive computer play, which is designed to train balance such as Nintendo Wii balance board, during the study period. As there is no strong research evidence that commercial computer games are effective in improving the balance for children with CP and this type of commercial computer play is not a routine training exercises for balance in the treatment sessions at the schools, it is believed that discontinuing this type of 'training' for 6 weeks would not cause detrimental effect on the balance of the study children.

All the assessment will be carried out by a blinded assessor (PA), who is not aware of the group allocation of the children. All the children will be assessed at the beginning, and 3, 6 and 12 weeks after the commencement of the intervention. The last assessment aims to examine the medium-term effect on their trunk control post-intervention.

Intervention:

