All participating children will be calibrated using the Tymo in a static sitting position in each treatment session by the research staff. Force and weight distribution will be calibrated by asking the child to move the trunk forward, backward and sideways as far as s/he can. The amplitude of the force and weight distribution between the two sides of the body will be recorded. These

information will be used to set up the Tymo as a balance training module (the intervention) by the software, in which the child will move the trunk forward, backward and sideways to participate in a computer game in a sitting position (Tables 1 and 2). The child will be allowed to choose which game they want in each treatment session and they have to stay on the same game for at least 10 minutes before changing to another game. In other words, the child will have a maximal choice of 2 computer games in each treatment session. All children will start at a medium level of difficulty. Only if the child is unable to score any point in 3 trials in a row, the difficulty level will be reduced to one level down. Similarly, if the child scores full points in 3 trials in a row, the difficulty level will be increased to one level up. The progression of the intervention will then be closely monitored by the research staff. A logbook will be used for each child to record the level of difficulty in each treatment session, the number of treatment sessions, duration of each session and general comments on the child in each session during the intervention phase. The intervention will be supervised by a research assistant, who will be employed for the study.

(iv) Data processing and analysis

Statistical analyses: SPSS for Windows (version 20) will be used to analyse the results. Mann Whitney U test will be used to compare the results of the OM(1) between the intervention and control groups and independent t-test for OM(2) to OM(5). The statistical significance level is set at $p < 0.05$.

[Word Court: 3814]

e) Existing Facilities:

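### The planned two-group tests leave out baseline as a covariate and school as a stratum, and do not define which result is tested; a single pre-chosen test would be valid, but precision is lost in a 20-child trial

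*Combined protocol and SAP*

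**What the plan says.** All references are to the combined protocol and SAP.

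- **Analysis, d)(iv).** "Mann Whitney U test will be used to compare the results of the OM(1) between the intervention and control groups". Independent t-tests are planned for outcomes (2) to (5), with significance at p < 0.05. Neither sentence says whether the result compared is the follow-up score or the change from baseline, or at which visit.
- **Baseline, d)(iii).** "After the initial assessment, all study children will be randomly allocated into a control group or treatment group", so a pre-randomisation value is planned for every child.
- **School, d)(iii).** Randomisation is done within each of two schools, "so as to take into account the heterogeneity of the children and treatment regime in each school".
- **Visits, d)(iii).** Assessments are at weeks 0, 3, 6 and 12. Of week 12 the plan says: "The last assessment aims to examine the medium-term effect on their trunk control post-intervention".
- **Hypotheses, c).** All four concern improvement after six weeks of training. That points to change at week 6, but d)(iv) does not make the link.
- **Scores, d)(ii).** For SATCo, "The trunk control is tested under 3 different conditions in sitting". For PRT, "how far the child can reach forward, to right and to left will be measured in sitting and standing". No single score is named for either test.
- **Size.** Section d)(i) sets 10 children per arm without a calculation. Section g) gives 20 per arm.

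**The concern.** The design collects two pieces of information that normally sharpen a group comparison, and the analysis names neither. Baseline can enter the planned tests only if the results are read as change scores, and then only by subtraction. School, which governs the randomisation, does not enter at all. With 20 children and no power calculation, recovering precision from data already planned is one of the few improvements open to this trial, and section g) presents it as overcoming the small samples and weak designs of earlier studies.

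The second issue is error control. The wording leaves open follow-up or change, the visit, and the SATCo condition. If any of these is settled after the data are seen, the nominal 5% no longer applies to the primary outcome.

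**Working it through.** **Inputs.** From the plan: 10 per arm and alpha 0.05. Assumed: two-sided tests, 80% power, equal schools. The plan gives no effect size, SD or power, so there is no sample size calculation to reproduce.

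No baseline-to-week-6 correlation is given for any outcome, so every rho below is an assumption. The PRT test-retest figure ("intraclass correlation coefficients= 0.54 to 0.88") suggests scanning 0.54 to 0.88. For GMFM-88 the section cites rater "reliability of the GMFM 88 have been shown to be very high (ICC= 0.99 in both cases"), so I scan up to 0.95. Reliability is only a rough guide to rho.

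**Formulas.** With n per arm and N = 2n, the detectable effect in outcome SDs is δ(df) × √(2/n) × √V, where δ is the 80%-power noncentrality of the t-test.

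- Follow-up score: V = 1, df = N − 2.
- Change score: V = 2(1 − rho), df = N − 2.
- ANCOVA on baseline and school: V = (1 − rho²)(1 + 1/(N − 5)), df = N − 4.

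**Worked at n = 10, rho 0.54.** δ(18) = 2.963, δ(16) = 2.985, √(2/10) = 0.4472.

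- Follow-up: 2.963 × 0.4472 = 1.32.
- Change: 1.325 × √0.92 = 1.27.
- ANCOVA: V = 0.7084 × 1.0667 = 0.7556, so 2.985 × 0.4472 × √0.7556 = 1.16.
- Variance against change: 0.7556/0.92 = 0.82, that is 18% lower.

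| rho | Follow-up | Change | ANCOVA |
|---|---|---|---|
| 0 | 1.32 | 1.87 | 1.38 |
| 0.54 | 1.32 | 1.27 | 1.16 |
| 0.70 | 1.32 | 1.03 | 0.98 |
| 0.88 | 1.32 | 0.649 | 0.655 |
| 0.95 | 1.32 | 0.42 | 0.43 |

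**Break-even.** Against follow-up scores ANCOVA wins above rho of about 0.28, with no upper limit. Against change scores, with no school effect on change, it wins below 0.85 at 10 per arm, 0.79 at 8 and 0.51 at 5. At the 20 per arm of section g) that limit would be about 0.94. Beyond break-even at 10 per arm the loss is about 0.01 SD.

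**Validity.** In simulation with no school effect, the unadjusted t-tests had type I error of 4.8-5.1% and Mann-Whitney 3.7-5.1%. Ignoring a school shift made the follow-up tests conservative: about 4.3% at 0.5 SD and 2.8% at 1 SD.

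**SATCo.** Latent normal scores were cut into 3 to 8 levels, with 10 per arm; the cut-points are assumptions. Power of Mann-Whitney on change against rank-ANCOVA (week-6 ranks on group, baseline ranks and school):

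- 0.8 SD shift, rho 0.54: gain of 9-12 points (33% to 44% with eight equally likely levels; 16% to 26% with three).
- 0.4 SD shift, rho 0.54: gain of about 2-3 points.
- 0.4 SD shift, rho 0.95, eight equally likely levels: loss of about 2 points (53% to 51%). A separate 8-level simulation lost about 5 (63% to 58%).

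Against Mann-Whitney on follow-up, the gain at rho 0.54 with few levels is about 1-3 points (24% to 26% with three levels, 0.8 SD shift). At high rho it is large (24% to 67% with eight levels at rho 0.9).

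**Open choices at week 6, no true effect.** Taking whichever of follow-up or change is significant gives 9.2-9.8% false positives with t-tests and 8.5-9.4% with Mann-Whitney. If the SATCo condition is also open, Mann-Whitney gives 16-23%, assuming between-condition correlations of 0.5 to 0.9. Rank-ANCOVA with the condition still open gives 10-14%, so adjustment does not replace naming the score.

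**The case against.** The strongest reply is that this is largely a preference. A simple pre-chosen test is valid, this is a pilot, and on the likelier reading (change at week 6) baseline is already used by subtraction. The gain over change is then modest, absent at the correlations likely for GMFM-88, and absent at about 5 per arm. All of this stands, and it limits the size of the point.

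A reader might infer more than the documents support:

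- **That the tests ignore baseline altogether.** Section d)(iv) does not define the result, and section c) speaks of improvement. One can say only that baseline is not a covariate and school is not in the analysis.
- **That the tests are invalid.** They are not. Leaving out school makes them slightly conservative if the schools differ.
- **That adjustment always helps SATCo.** The gain depends on rho, the number of levels, the true shift and the comparator, and it can turn into a small loss.
- **That the school term brings a large gain.** With an assumed 0.5 SD school gap in change at rho 0.88, power for a 0.8 SD effect is 89% unadjusted and 93% with ANCOVA. But the SD of change there is √(2 × 0.12) = 0.49, so the assumed gap is a full SD of change. The plan says the schools differ, not by how much.
- **That the sponsor means to choose after seeing the data.** Nothing says so. The text simply does not prevent it.

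SATCo scoring may be laid down in the publication the plan cites. Even so, the plan should say which score is tested.

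**Conclusion.** The concern holds in a limited form. The analysis names neither baseline as a covariate nor the school stratum, and this costs precision over much of the assumed range of rho. At 10 per arm and rho 0.54 the detectable effect falls from 1.27 SD (change) or 1.32 SD (follow-up) to 1.16 SD. If follow-up scores are what is meant, the loss is large at high rho (1.32 against 0.655 SD at 0.88). If change is meant, the gain ends near 0.85 and is lost sooner with fewer children. For SATCo the gain is usual but conditional.

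The undefined result is the firmer part. It needs no assumption about rho to see that the error rate of the primary outcome is unprotected until the score, condition and visit are fixed. The plan should be changed before analysis, but nothing here makes a single pre-chosen test wrong. Confidence is medium, because every rho and every SATCo distribution is assumed.

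**What to change.** In section d)(iv):

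1. Make week 6 the primary time point, in line with the hypotheses, with weeks 3 and 12 secondary.
2. Name one primary SATCo score in advance (static, active, reactive, or a stated total). Analyse it by rank-ANCOVA of the week-6 score on group, baseline rank and school. Show arm medians at baseline and week 6 descriptively. Do not present a Hodges-Lehmann interval for change as the interval belonging to this test, since the two can disagree.
3. Analyse PRT and GMFM-88 by ANCOVA of the week-6 value on group, baseline and school, and report the adjusted difference with 95% CI. Name one PRT score. Where rho is very high the expected loss is about 0.01 SD, which is a small price for one consistent rule that respects the randomisation.
4. For outcomes that only a few children may be able to perform (standing PRT, 2-minute walk), report the numbers analysed and give the estimate with CI as descriptive. At an assumed 5 per arm and rho 0.54 adjustment brings nothing (1.96 against 1.94 SD for change).
5. Describe height and weight by arm without a test, as no hypothesis concerns them.
6. Reconcile the 20 per arm in section g) with the 10 per arm in d)(i) and d)(iii).

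**Cost.** SAP wording and standard commands in the software already planned; no new data. The model uses two degrees of freedom, or three if the reserve school in section e) is opened. There is a slight loss if rho is near 0 (1.38 against 1.32 SD for follow-up scores) or very high (0.43 against 0.42 SD for change at 0.95).

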game will be adjusted according to the information provided during the assessment so that the user needs to move their body accordingly in different directions without losing their balance. This equipment is specially designed for rehabilitation for people with movement disorders, hence unlike the commercial games, there are no flashing lights or sudden noises during the games. To our best knowledge, there has been no study published using Tymo as an intervention for training trunk control in children with CP.

c) Aims and Hypotheses to be Tested:

Conducting a pilot single-blinded randomised controlled trial (RCT), the overall objective is to investigate the effect of a 6-week training programme using an interactive computer play training tool on the segmental trunk control, sitting and/or standing balance and gross motor function in children with CP.

The hypotheses to be tested are:

- (1) That after 6 weeks of training using the interactive computer play training tool, Tymo, the children with CP will show significant improvement in their segmental trunk control as demonstrated in the SATCo.
- (2) That after 6 weeks of training using the interactive computer play training tool, Tymo, the children with CP will show significant improvement in their balance in sitting and/or standing positions as demonstrated in the PRT.
- (3) That after 6 weeks of training using the interactive computer play training tool, Tymo, the children with CP will show significant improvement in gross motor activities as demonstrated in the GMFM 88.
- (4) That after 6 weeks of training using the interactive computer play training tool, Tymo, children with CP, who are able to ambulate independently with a walking aid, will show a significant improvement in the distance covered in 2 minutes.

d) Plan of Investigation:

(i) Subjects

Selection criteria:

- (1) Children with a diagnosis of CP will be of GMFCS levels III to IV, who in general, require walking aid (level III) during ambulation and with limited walking ability (level IV).^[4] Aiming to achieve a higher homogeneity of the recruited children, for those with level III, only those requiring physical assistance to climb stairs will be recruited and so it is believed that only those with lower motor ability, i.e. similar to level IV, will be included.
- (2) Children, with non-CP physical disabilities, will have similar gross motor function as in (1).
- (3) Aged from 6 to 12 years old and

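### Must section d)(iv) name the SATCo score, and value or change, for the primary comparison?

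*Combined protocol and SAP*

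**What the plan says.** Section d)(ii) makes SATCo the only primary outcome, OM(1). Support is lowered step by step through seven levels, from head control down to "pelvis (lower lumbar) and no support to measure full trunk control". The same section adds that "The trunk control is tested under 3 different conditions in sitting": static, active and reactive. It gives no total, no rule for combining the three, and no deciding condition.

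Section d)(iii) sets the visits: "All the children will be assessed at the beginning, and 3, 6 and 12 weeks after the commencement of the intervention". It gives the week-12 visit a separate purpose: "The last assessment aims to examine the medium-term effect on their trunk control post-intervention".

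Hypothesis (1) in section c) fixes the time point in these words: "6 weeks of training using the interactive computer play training tool, Tymo, the children with CP will show significant improvement in their segmental". The sentence ends by naming SATCo as the measure.

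The analysis in section d)(iv) is then a single clause: "Mann Whitney U test will be used to compare the results of the OM(1) between the intervention and control groups". The significance level is 0.05, with no statement on sidedness or multiplicity. The sample is 20 children, 10 per arm, set on feasibility and without a power calculation (section d)(i)).

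**The concern.** A Mann-Whitney test needs one number per child, and the plan does not define that number. With three conditions, and value or change for each, six analyses at week 6 all fit the wording. If the choice were made once results were visible by group, the most favourable could be reported as the primary result, and the nominal 5% would no longer describe the chance of a false claim.

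The point is not idle. Section g) looks ahead to the intervention being shown to work and added to conventional physiotherapy, and it presents SATCo's sensitivity to small segmental changes as a strength of the study. Blinding the assessor, as section d)(iii) does, protects the measurements but not the later choice of which one to test.

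**Working it through.** **What the documents settle.**

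- Visit: hypothesis (1) refers to the end of 6 weeks of training, and week 12 is described as medium-term. Week 6 is therefore the primary time point.
- Test and level: Mann-Whitney, between groups, 0.05.
- Left open: the score (static, active, reactive or a summary) and the form (week-6 value or change from baseline). That makes 3 conditions × 2 forms = 6 candidate tests, before any summary score is considered.

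**What the open choice could do to the error rate.** There is no stated figure to reproduce, because the plan gives no effect size, SD or power. The calculation is therefore conditional.

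If k independent tests are each run at 0.05 and any one may count, the chance of at least one false positive is 1 − 0.95^k:

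- k = 3: 1 − 0.95³ = 14.3%
- k = 6: 1 − 0.95⁶ = 26.5%

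Scores from the same child are correlated, so these are upper illustrations. Simulation under no effect used 10 per arm, the tie-corrected asymptotic Mann-Whitney test, two-sided 0.05, and assumed correlations between conditions from 0 to 0.95:

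| Spread of children over levels | One score | Any of three conditions |
|---|---|---|
| Seven equally filled levels | 4.7-5.0% | 13.9% falling to 8.0% |
| Three levels, 20/60/20 | 4.4-4.7% | 13.0% falling to 9.3% |
| Three levels, 10/80/10 | 3.3-3.5% | 9.6% falling to 7.0% |

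A continuity correction lowers these. With seven equal levels the any-of-three rate becomes 12.8% falling to 7.3%. With 10/80/10 it becomes 6.0% falling to 4.2%.

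For one score with value or change both allowed to count, the rate is 8.4-9.6% with seven equal levels (7.6-8.8% with continuity correction), for assumed baseline to week-6 correlations of 0.3-0.9. With all six week-6 tests open, it is about 17-19% on a continuous scale at assumed correlations of 0.5-0.8.

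**Reading the table.** The one-score column applies to a plan that makes one comparison, whichever score is used. It never exceeds 5%. The right-hand column needs an additional rule, that any one significant condition is enough, and section d)(iv) states no such rule.

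**Whether the documents favour one form.** Take an assumed 1.0 SD shift and a baseline to week-6 correlation of 0.7. Power for change against value is 59% v 51% with seven equal levels, 45% v 44% at 20/60/20, and 35% v 37% at 10/80/10. The order depends on how the children spread over the levels, which the documents do not give. No form can be called right from this plan.

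**The case for a change.** The strongest contrary case is that even the most favourable reading, one test, still needs a defined variable, and there is none. The team's knowledge of the instrument (section e) says the co-applicant developed SATCo) is not the same as a written choice. The wording of hypothesis (1) leans towards change, whereas section d)(iv) speaks of comparing results, which reads more naturally as values. Writing the choice down would cost a sentence, and after outcomes are seen by group it could no longer be made credibly.

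Most of this stands as description. The score and the form are unstated, and neither hypothesis (1) nor the baseline visit settles them. What does not stand is the step from an unstated detail to an inflated error rate. That step assumes several SATCo results would be tested and the best one claimed, which the plan neither says nor implies. Whether the cited SATCo publication supplies a standard score cannot be judged from these documents, so it counts for neither side.

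**Conclusion.** No change to the plan is called for. The gap is genuine but is one of missing detail. No rule that the plan states leads to a wrong result. One between-group test at 5% fits the wording at least as well as three, and it holds the error rate at about 5% or slightly below for any score or form chosen without sight of the group results. The higher rates, about 7-14% for any of three conditions and 8-10% for value or change with evenly filled levels, describe selection after the fact and not the plan. They rest on assumed correlations, assumed spreads over the SATCo levels and two-sided testing.

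A revision would only ask the team to record a choice that is already its own, and the power comparison gives no basis for steering that choice. In a 20-child pilot sized on feasibility, an analyst can reasonably settle the score and form before comparing the groups, and report which were used. The caution for readers of the results is narrow: if several SATCo results are reported and only one is significant, that one should not be read as a 5% test.

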Both the PA and co-applicant are very experienced paediatric physiotherapists with over 20 years of experience in managing young children with movement disorders. The mother institution of the PA is the only University in Hong Kong running the undergraduate degree in Physiotherapy and the Department of Rehabilitation Sciences at the Hong Kong Polytechnic University has abundant experiences in conducting research studies on individuals with movement disorders. Space will be provided for data storage (both hard and soft data) and statistical software will be provided for the present study. The co-applicant is the developer of the SATCo and is active in conducting research studies with collaborating researchers in USA and Denmark in examining trunk control in children with CP.

The Medical Technologies Ltd is the sole agent in Asia, which manages the Tymo Therapy plate. The agent will provide training and support in using the Tymo Therapy plate to all relevant personnel in this study in Hong Kong, as part of their quote on the equipment.

Initial contact has been made with the physiotherapists in-charge at 3 special schools in Hong Kong, namely the John F Kennedy Centre, the Red Cross Princess Alexandra School and Pui Oi School (all are special schools for children with physical disabilities), who all show interests to participate in the study. Specifically, the study children will be recruited from the first two schools and these schools will accommodate the Tymo Therapy Plate on site during the intervention phase. The physiotherapists in-charge tentatively believed that recruitment of 20 children with CP or similar physical disabilities is feasible in the first 2 schools. In case the recruitment falls short or a substantial drop-outs during the study period, Pui Oi School would be approached for further recruitment.

f) Justification of Requirements:

Staffing- a Physiotherapist will be employed to supervise the children to carry out the ICP at respective schools. Salary for this personnel is set as point 19 (median point of Physiotherapist II) of MPS, i.e. \$32,560 per month + \$1,500 MPF per month for 6 months= \$204,360 because the personnel is required to have experience in managing paediatric clients with physical disabilities and has

understanding of postural control in children.

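### Four assessments per child are collected, but only one-value-per-child tests are planned, with no visit, score form or missing-data method, so a child lost before week 6 or 12 drops out of that comparison

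*Combined protocol and SAP*

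**What the plan says.** Section d)(iii), Study design, sets four assessments: "All the children will be assessed at the beginning, and 3, 6 and 12 weeks after the commencement of the intervention". It gives the week-12 visit its own purpose: "The last assessment aims to examine the medium-term effect on their trunk control post-intervention".

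Section d)(iv), Data processing and analysis, holds the whole analysis plan. For the primary outcome, "Mann Whitney U test will be used to compare the results of the OM(1) between the intervention and control groups". For PRT, GMFM 88, the 2-minute walk test and height and weight, it names the "independent t-test for OM(2) to OM(5"). It then gives the software and the significance level. It does not name a visit, a score form (raw or change), an analysis set, a repeated-measures method or a missing-data method.

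The week-6 focus comes from section c), where each hypothesis refers to the end of the 6-week training.

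Drop-out is mentioned once, in section e), Existing Facilities, as a contingency: "In case the recruitment falls short or a substantial drop-outs during the study period", a third school would be approached for more children. No drop-out rate is assumed.

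**The concern.** Both named tests take one value per child. A child seen at week 3 but missing at week 6 has no value to enter, and the week-3 result, which says how that child was doing, is not used.

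Only the treated arm carries the training load, 4 sessions a week for 6 weeks, or 24 sessions. Unequal loss is therefore plausible, although the documents give no rate. If treated children who are doing less well are the ones who go unassessed, those left could make Tymo look better than it is. Recruiting from a third school adds children, but it neither recovers the leavers' information nor restores the comparison as randomised.

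The medium-term aim has an assessment but no stated contrast.

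**Working it through.** **Inputs from the documents.** 10 children per arm (section d)(i)); visits at 0, 3, 6 and 12 weeks; two-sample tests; significance at 0.05, taken as two-sided. The plan gives no effect size, SD, power or drop-out rate, so it has no figure of its own to reproduce.

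**Assumptions.** No true effect, normal scores with SD 1, loss in the treated arm only, occurring after week 3. Loss rates and correlations are illustrative.

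**1. Loss on the same scale as the tested score.** Suppose treated children below the week-3 mean leave with probability p. The expected number lost is 10 × p/2. The mean week-3 score of those who stay is 0.399p / (1 − p/2), where 0.399 is the standard normal density at zero. The spurious week-6 difference is the week-3 to week-6 correlation ρ times that mean.

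| p | Lost of 10 | Mean shift at week 3 | Bias, ρ = 0.6 | Bias, ρ = 0.8 |
|---|---|---|---|---|
| 0.2 | 1 | 0.089 | 0.053 | 0.071 |
| 0.4 | 2 | 0.199 | 0.120 | 0.160 |
| 0.6 | 3 | 0.342 | 0.205 | 0.274 |

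Simulation with 10 per arm (40,000 trials per setting) gives the same picture: 0.052, 0.120 and 0.209 SD at ρ = 0.6, and 0.069, 0.157 and 0.276 SD at ρ = 0.8. The false-positive rate is 5.1, 5.8 and 6.8%, and 5.3, 6.3 and 8.4%. An estimate that also uses week 3 has bias of 0.007 SD or less.

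For scale, the standard error of the difference is √(1/9 + 1/10) = 0.46 SD with one child lost and √(1/7 + 1/10) = 0.49 SD with three lost. The largest bias is therefore a little over half a standard error (0.276/0.49 = 0.56).

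**2. Other loss rules.** Now add baseline, with equal correlation ρ between all visits.

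- Loss by week-3 gain, raw week-6 score tested: the covariance is ρ − ρ = 0, so there is no bias.
- Loss by week-3 level, change from baseline tested: the covariance is again ρ − ρ = 0, so there is no bias.
- Loss by week-3 gain, change tested: the bias is √((1 − ρ)/2) times the shifts in the table. It runs from 0.316 × 0.089 = 0.03 (ρ = 0.8, one lost) to 0.447 × 0.342 = 0.15 raw-score SD (ρ = 0.6, three lost). Simulated rejection is 5.0 to 6.2%.
- Random loss, or the same rule at the same rate in both arms: about 0.

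So the 0.05 to 0.28 SD range requires the loss rule and the tested score to be on one scale, with correlation 0.6 to 0.8 on that scale.

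**3. Loss tied to the unseen result.** Suppose the 20% of treated children with the smallest week-6 gain leave, no control leaves, and ρ is 0.5 to 0.9. The change-score bias is √(2(1 − ρ)) × 0.350 = 0.16 to 0.35 SD. In simulation, a model using baseline and week 3 of every child still leaves 0.13 to 0.27 SD.

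**4. Baseline adjustment.** A model with unconstrained arm-by-visit means gives a week-6 contrast that is not adjusted for baseline. At ρ = 0.8 with one child lost, its spread is about 0.46 SD. A change score gives 0.46 × √(2 × 0.2) = 0.29 SD. A mixed model without baseline as covariate or constraint would give up that precision.

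**5. Week 12.** Take a true effect of 0.8 to 1.0 SD that is fully retained, with no loss and week-6 to week-12 correlation 0.7 to 0.9. Of trials significant at week 6, 13 to 32% are not significant at week 12. This mainly reflects low power: a 1 SD difference is detected 56% of the time with 10 per arm.

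**The case against.** A reader might infer that the plan expects drop-outs, prescribes a separate test at each visit, and will therefore give biased results. The documents do not support this. Drop-out is an in-case contingency. No visit is named, so per-visit testing is an inference from silence. Bias also needs loss that is both response-related and unequal between arms.

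A child who stops training need not miss assessment. Training takes place at school, the plan says all children are assessed at every visit, and assessor trips are budgeted. The documents offer no basis for a particular rate of one-sided missing assessments. With one child lost, the bias of 0.05 to 0.07 SD is small against a standard error of 0.46 SD, in a 20-child pilot sized on feasibility.

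A reader might also infer that fading or persistence will be judged by which p-values cross 0.05. Nothing says so, and a between-arm comparison at week 12 is a fair reading of the medium-term aim.

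These objections stand, and they limit how strongly the point can be put. They do not answer the gap itself: four visits are collected, and the plan neither chooses among them nor says what happens when one is missing.

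**Conclusion.** The point holds as a conditional weakness that should be fixed. The named tests, applied to children present at week 6 or 12, ignore leavers' earlier visits, and nothing in the plan compensates. Under assumed one-sided loss of 1 to 3 of 10 treated children, the bias is about 0.05 to 0.28 SD when loss follows the scale of the tested score. It is about 0 when loss is random or follows a different scale. The rates, correlations and loss rules are assumptions. The gap covers the primary Mann-Whitney test as well as the secondary t-tests, and the week-12 aim concerns trunk control, so SATCo must be included. A repeated-measures model removes bias only from loss explained by observed data.

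**What to change.** - For PRT, GMFM 88 and the walk test, replace the t-tests with one repeated-measures mixed model per outcome. Use the week 3, 6 and 12 values of all randomised children (for the walk test, those able to walk, as in hypothesis 4).
- Include visit, arm and arm × visit, with the baseline value as covariate or the arm means constrained equal at baseline. Use Kenward-Roger or Satterthwaite degrees of freedom where the software offers them, and a simple covariance structure if the unstructured one does not converge.
- Name the week-6 contrast as the test, in line with the hypotheses.
- For the medium-term aim, report the week-12 contrast and the between-arm difference in change from week 6 to week 12, each with a 95% CI, including for SATCo.
- For SATCo, keep the rank test at week 6, state its score form, and add the same model on the level score as a supporting analysis.
- Keep replacement children distinguishable in the data, and retain everything collected from those who left.
- Add a short sensitivity analysis for loss tied to unseen outcomes, for example shifting the missing treated values over a stated range.

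The cost is analysis wording and modest programming on data already scheduled. The downside is that a covariance structure must be assumed with only 20 children.
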